### **3.1. Screening/Baseline data collection**

Prior to randomization, children must have an HIV test. There is no specific time period within which the HIV test must have been performed. If the test is negative, they will be eligible for randomization

Baseline data will include:

- Informed consent type and date
- Birth month/year and gender
- Urine pregnancy test result for females who are of childbearing potential, i.e., females who have experienced menarche or who are aged 14 years and older
- High risk occupation (e.g., work involved or might involve contact with living or dead persons with Ebola such as a nurse, physician, ambulance driver, burial crew member or other healthcare worker or not a healthcare worker)
- History of past contact with a person with EVD
- Name and contact information for participant (to be kept locally)
- Names and contact information of 2 alternate contact people (to be kept locally)
- Body temperature
- Height and weight
- Mid-upper arm circumference (for children 1-5 years).
- Serum for aspartate transaminase (AST), alanine transaminase (ALT), creatinine, and potassium
- Blood for CBC with differential, platelet count, hemoglobin, hematocrit, mean corpuscular volume (MCV), and red cell distribution width (RDW)
- Blood for assessing HIV and syphilis serostatus
- Stored serum for immunogenicity testing and future research
- Stored cells for assessing T cell and memory B cell function (subsample of adults enrolled at a single site in Guinea)
- Stored saliva for assessing viral shedding (subsample of children)
- Antipyretics prescribed/offered

### **3.2. Vaccine administration**

Following informed consent and the collection of baseline data, the study vaccines will be administered to participants who meet all of the eligibility criteria via intramuscular injection in the upper, outer aspect of the arm (deltoid region). Children may be vaccinated in the thigh. Prior to injection, the area to be injected will be prepared using an alcohol swab. Vaccine will be administered using a 3 mL syringe with a sterile needle. While holding the needle at an approximate 90-degree angle to the skin, the needle will be directed through the skin, into the

muscle of the arm (or thigh). The location of vaccination will be recorded on the case report form.

At the time of prime vaccination administration, the tear-off portion of the SID label on the syringe will be placed on the baseline CRF.

Study participants/family members will also be provided information on how to minimize risk of infection with Ebola.

After vaccination, participants will be watched closely for at least 30 minutes. Injection site reactions, targeted symptoms of any grade severity, and grade 3 and 4 AEs that occur during this observation period will be recorded.

Participants may be offered medication post-vaccination for fever and pain relief depending on each site's policy. If participants receive or take their own medication for fever and pain following vaccination, it will be recorded.

The same procedures will be followed for the MVA-BN-Filo and rVSVΔG-ZEBOV-GP booster/placebo vaccination at 56 days. As stated below, the window for the booster vaccination at 56 days is 53 to 66 days (-3,+10 days).

### **3.3. Follow-up data collection**

Following randomization, all participants will be seen at the following visits (visit window): 7 ( $\pm 3$  days), 14 ( $\pm 3$  days), 28 ( $\pm 7$  days), 56 (53 to 66 days) and 63 days (7  $\pm 3$  days after the booster vaccination), and at 3 ( $\pm 14$  days), 6 ( $\pm 1$  month), and 12 ( $\pm 1$  month) months. Participants may continue to be seen at 24 ( $\pm 1$  month), 36 ( $\pm 1$  month), 48 ( $\pm 1$  month) and 60 ( $\pm 1$  month) months if funding permits.

At each follow-up visit, volunteers will be asked a few questions to assess the development of any serious medical conditions (e.g., malaria), the possibility of unreported SAEs, and for women whether they are pregnant. Temperature will be recorded, and blood will be drawn for immunogenicity testing and future research.

The following additional information will be collected at 7, 14, 28, and 63 days and at 3 months (approximately 35 days after the booster) following randomization:

- Grade 3 and 4 AEs and targeted symptoms since vaccination
- Injection site reactions since vaccination

The following additional specimens and information will be obtained for children: 1) during the first week following the prime and booster vaccination, there will be daily contacts with children to assess injection site reactions, targeted symptoms and SAEs, and to measure temperature; 2) on day 7 and 63, serum for AST, ALT, creatinine, and potassium and blood for CBC with differential, platelet count, hemoglobin, hematocrit, MCV, and RDW will be obtained; 3) on day 28, at months 3 and 6 and annually weight will be recorded; 4) annually height will be measured;

and 5) mid-upper arm circumference (children aged 1-5 years) will be measured at months 3, 6, and 12, and then annually if funding permits.

For a subsample of adults, at baseline and days 7, 14, 56, 63, 70, and month 12, cells for assessing T cell and memory B cell function will be obtained. If funding permits, cells will also be collected at 24, 36, 48 and 60 months,

On day 56 prior to the booster vaccination, a urine pregnancy test will be performed for females of child-bearing potential, i.e., females who have experienced menarche or who are aged 14 years and older. If a woman is pregnant, she cannot receive the booster vaccination. However, she will remain under follow-up.

Following the booster vaccination, participants will be watched closely for at least 30 minutes. Injection site reactions, targeted symptoms of any grade severity, and grade 3 and 4 AEs that occur during this observation period will be recorded.

After 12 months of follow-up have been completed for all participants, participants will be informed which vaccine they received and the results of the study.

### **3.4. Laboratory Tests**

Safety laboratory tests will be performed by a clinical laboratory at the site.

Safety laboratory reports will be generated and returned to the vaccination center(s) prior to the next scheduled visit.

At one site peripheral blood mononuclear cells (PBMCs) will be collected for a subsample of adults and stored for the investigation of T cell and memory B cell responses.

At one site saliva will be collected for a subsample of children for measurement of viral shedding.

Immunogenicity testing will be performed using a validated FANG GP-ELISA assay on baseline, Day 28, Month 3 and Month 12 specimens. The participating pharmaceutical companies will be provided samples from these visits and have the primary responsibility for obtaining this testing. A non-validated FANG GP-ELISA assay or another assay may also be used at these and other time points.

### **3.5. Biometric Data**

Digital finger prints and iris scans may also be collected, digitized and stored in a secure database. These data would be used to ensure appropriate matching of study participants with PIDs.

## **4. ASSESSMENT OF SAFETY**

A manual of operations will describe procedures for reporting deaths, Ebola events, pregnancies, pregnancy outcomes, and SAEs, including assessments of severity and the relationship of the vaccine to events. Below a brief summary is provided.

## **4.1. SPECIFICATION OF SAFETY PARAMETERS**

### **4.1.1. Definition of AE**

An AE is any untoward medical occurrence in a randomized volunteer who is administered the trial product (vaccine or placebo), whether or not considered related to the vaccination.

### **4.1.2. Definition of an Adverse Reaction (AR)**

An AR is any untoward and unintended response related to an investigational medicinal product (in this case, vaccine or placebo).

### **4.1.3. Definition of SAE**

An AE is considered "serious" if, in the view of either the investigator or sponsor, it results in any of the following outcomes:

- a. Death
- b. Events that are life-threatening

Note: The term 'life-threatening' in the definition of 'serious' refers to an event in which the participant was at risk of death at the time of the event. It does not refer to an event, which hypothetically might have caused death, had it been more severe.

- c. Events requiring hospitalisation
- d. Events requiring prolongation of existing hospitalisation,

Note: In general, hospitalization signifies that the participant has been admitted at the hospital or emergency ward for observation and/or treatment that would not have been appropriate in the physician's office or in an out-patient setting. Complications that occur during hospitalization are also considered as SAEs. If a complication prolongs hospitalization or fulfils any other serious criteria, the event will also be considered serious. When in doubt as to whether 'hospitalization' occurred or was necessary, the AE should be considered serious.

Hospitalization for elective treatment of a pre-existing condition (known or diagnosed prior to informed consent signature) that did not worsen from baseline is NOT considered an SAE.

- e. Events resulting in a persistent or significant incapacity or substantial disruption of the ability to conduct normal life functions

Note: The term disability means a substantial disruption of a person's ability to conduct normal life functions. This definition is not intended to include experiences of relatively minor medical significance such as uncomplicated headache, nausea, vomiting, diarrhea, influenza-like illness, and accidental trauma (e.g. sprained ankle) which may interfere or prevent everyday life functions but do not constitute a substantial disruption.

- f. Congenital anomaly or birth defects in the offspring of a study participant
- g. Important medical events, that may not result in death, be life-threatening, or require hospitalization may be considered serious when, based upon appropriate medical judgment, they may jeopardize the participant and may require medical or surgical intervention to prevent one of the outcomes listed in this definition. Examples of such medical events include:
- Any suspected transmission of an infectious agent by a medicinal product
  - Allergic bronchospasm requiring intensive treatment in an emergency room or at home
  - Blood dyscrasias or convulsions that do not result in inpatient hospitalization
  - Development of drug dependency or drug abuse.
  - Cranial nerve disorders, including paralyzes/paresis (e.g. Bell's palsy)
  - Optic neuritis
  - Multiple sclerosis
  - Transverse myelitis
  - Guillain-Barré syndrome, including Miller Fisher syndrome, Bickerstaff's encephalitis and other variants
  - Acute disseminated encephalomyelitis, including site specific variants: e.g. non-infectious encephalitis, encephalomyelitis, myelitis, myeloradiculomyelitis
  - Myasthenia gravis and Lambert-Eaton myasthenic syndrome
  - Immune-mediated peripheral neuropathies and plexopathies, (including chronic inflammatory demyelinating polyneuropathy, multifocal motor neuropathy and polyneuropathies associated with monoclonal gammopathy).
  - Narcolepsy
  - Isolated paresthesia of >7 days duration

Note: For this protocol, EVD events and laboratory confirmed malaria events that do not require hospitalization will not be considered as SAEs. Laboratory diagnostic criteria for confirmation of malaria should be based on local criteria.

#### **4.1.4. Serious Adverse Reaction (SAR)**

Any AR which is also considered serious.

#### **4.1.5. Suspected Unexpected Serious Adverse Reaction (SUSAR)**

An AR that is both unexpected (not consistent with the applicable product information) and also meets the definition of a SAR.

#### **4.1.6. Definition of Unanticipated Problems (UP)**

An UP is any incident, experience or outcome that meets all of the following criteria:

1. Unexpected in terms of nature, severity, or frequency in relation to:

- a. the research risks that are described in the ethical committee/institutional review board (IRB)-approved research protocol and informed consent document; Investigator's Brochure or other study documents; and
  - b. the characteristics of the population being studied; and
2. Possibly, probably, or definitely related to participation in the research ("possibly related" means there is a reasonable possibility that the incident, experience, or outcome may have been caused by the procedures involved in the research); and
  3. Places study participants or others at a greater risk of harm (including physical, psychological, economic, or social harm) than was previously known or recognized.

Furthermore, a UP could be an expected event that occurs at a greater frequency in one of the vaccine groups than the placebo group.

## **4.2. CLASSIFICATION OF AN AE**

### **4.2.1. Relationship to study product**

The relationship assessment is one of the criteria used when determining regulatory reporting requirements.

Relationship of SAEs should be assessed by the site physician using the following question:

Is there a reasonable possibility that the AE may have been caused by the study product (vaccine)?

**YES** : The AE is known to occur with the study product, there is a reasonable possibility that the study product caused the AE, or there is a temporal relationship between the study product and event. Reasonable possibility means that there is evidence to suggest a causal relationship between the study product and the AE.

**NO** : There is not a reasonable possibility that the administration of the study product caused the event, there is no temporal relationship between the study product and event onset, or an alternate etiology has been established.

### **4.2.2. Unexpectedness**

Only SAEs will be assessed as expected or unexpected. An SAE will be considered unexpected if the nature, severity, or frequency of the event is not consistent with the risk information previously described for the vaccine.

An SAE is considered "unexpected" if it is not listed in the Investigator's Brochure or is not listed at the specificity or severity that has been observed; or, if an Investigator's Brochure is not required or available, is not consistent with the risk information described in the general investigational plan or elsewhere in the protocol, as amended.

*For example, under this definition, hepatic necrosis would be unexpected (by virtue of greater severity) if the Investigator's Brochure referred only to elevated hepatic enzymes or hepatitis. Similarly, cerebral thromboembolism and cerebral vasculitis would be unexpected (by virtue of greater specificity) if the Investigator's Brochure listed only cerebral vascular accidents.*

"Unexpected," as used in this definition, also refers to AEs or suspected ARs that are mentioned in the Investigator's Brochure as occurring with a class of drugs or as anticipated from the pharmacological properties of the drug, but are not specifically mentioned as occurring with the particular drug under investigation.

### **4.3. TIME PERIOD AND FREQUENCY FOR EVENT ASSESSMENT AND FOLLOW-UP**

#### **4.3.1. Time Period and Frequency Assessment**

##### **4.3.1.1. AE**

Injection site reactions, targeted symptoms of any grade severity, and unsolicited Grade 3 or 4 AEs will be collected and reported on CRFs as defined by the protocol (see [Appendix A](#)). AEs of grade 1 or 2 severity other than injection site reactions and targeted symptoms will not be collected. Grade 3 or 4 signs or symptoms associated with laboratory abnormalities and clinically significant grade 3 and 4 laboratory abnormalities documented by the investigators as AEs should be reported on the CRFs. All other laboratory abnormalities will be summarized using the protocol required laboratory data that is in the central database. Laboratory abnormalities that are considered clinically significant should be reported as AEs or SAEs irrespective of the presence of symptoms.

Sites will be notified of laboratory abnormalities identified as part of the protocol required testing (baseline for all participants and also 7 days after the prime and booster vaccination for children). Laboratory abnormalities will be summarized for each DSMB review. Details for documenting laboratory abnormalities in the participants medical record are provided in the manual of operations.

Injection site reactions will include redness of skin, swelling/induration, pain/tenderness with activity, and itching at injection site.

The targeted symptoms will include reduced activity/somnolence, fatigue, vomiting, chills, abnormal sweating, skin lesions (macules, papules, purpura, petechiae), mouth ulcers, decreased appetite, feverishness, diarrhea, nausea, headache, dizziness, abdominal pain, muscle pain, joint swelling, and joint pain.

For non-verbal children, subjective symptoms may not be assessed and irritability/fussiness, crying, and screaming will be assessed.

Injection site reactions and symptoms will be graded as follows: Grade 1 – symptoms causing no or minimal interference with usual social & functional activities; Grade 2 - symptoms causing greater than minimal interference with usual social & functional activities; Grade 3 - symptoms causing inability to perform usual social & functional activities; and Grade 4 - symptoms causing inability to perform basic self-care functions OR medical or operative intervention indicated to prevent permanent impairment, persistent disability, or death.

#### **4.3.1.2. SAEs, EVD events, Malaria Events**

SAE and EVD events will be assessed and reported on CRFs as soon as the site becomes aware of the event. For EVD events, where possible, a sample of blood will be stored for future research. Malaria events will be assessed at each follow-up visit. Malaria events that meet the SAE definition (e.g., result in hospitalization) will be reported on the SAE form.

#### **4.3.1.3. Pregnancy**

Women who report being pregnant in the first 3 months of follow-up after the prime vaccination will be followed for the outcome of their pregnancy.

The medical surveillance of the women and their children will be reinforced: a particular attention must be given to serious pathology occurring during pregnancy. An SAE form should be completed if an AE during pregnancy or birth outcome meets the SAE definition. Congenital anomalies or birth defects should also be reported as SAE.

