### **Procedures:**

Vaccination centers will be established in West Africa to consent, vaccinate and follow study volunteers. A case report form (CRF) with a unique participant identification code (PID) will be completed for each participant consented and randomized. The CRF may be paper or an electronic CRF (eCRF). The procedures described in this protocol are in terms of a paper CRF.

At the time of prime vaccination, a tear-off label on the syringe that includes a unique syringe identification code (SID) will be attached to the baseline CRF. The SID is a unique number from a centrally prepared randomization schedule. This will be the primary link between the blinded vaccine assignment and the PID. Study volunteers and clinical staff following the participants for safety and immunogenicity outcomes will be fully blinded.

At 56 days, a syringe with the corresponding PID will be prepared for each participant on his/her scheduled 56 day follow-up visit.

At study entry, study volunteers will be given an identification card that identifies them as study participants. The identification card will include contact information in the event they experience vaccine side effects or signs and symptoms of Ebola.

Participants will be instructed to avoid sharing items during the period of potential virus shedding. Women of childbearing potential will be told to use adequate birth control measures following randomization and until at least 3 months following the booster vaccination. Men who are sexually active with women of child-bearing potential will be told to use condoms following randomization and until at least 3 months following the booster vaccination.

Following randomization, all participants will be seen at 7, 14, 28, 56 and 63 days, and at 3, 6, and 12 months. The study will be unblinded after all participants have completed 12 months of follow-up. If funding permits, all participants will be seen annually through 60 months.

In addition, during the first week following the prime and booster vaccination, there will be daily contacts with participants < 18 years of age enrolled to assess injection site reactions and AEs graded for severity, including targeted symptoms, and SAEs.

Participants will be encouraged to contact the vaccination center by telephone if they have any AEs. If the participant experiences an AE requiring immediate attention, they will be given instructions on which hospital to go to for evaluation and treatment.

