### **5.4. Pregnancy**

Women who report being pregnant in the first 3 months of follow-up after the prime vaccination will be followed for the outcome of their pregnancy. The outcome will be reported on a CRF. Women who report being pregnant prior to the booster vaccination or who have a positive pregnancy test at 56 days will not receive the booster vaccination at 56 days.

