SAEs throughout follow-up	X	X
EVD events (reported as soon as aware) throughout follow-up and where possible a stored blood sample for future research	X	X
Death (reported as soon as aware) throughout follow-up	X	X
Pregnancy outcome for women who become pregnant in the first three months of follow-up after prime vaccination	X	X
a) Birth month and year, gender b) Contact information for self and 2 contacts who will know how to locate the volunteer c) Role as health care worker, contact with persons known to have EVD		

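### The rule for following pregnancies to outcome is worded two ways and runs only from the prime, so it ends 53-66 days before the protocol's own contraception period does

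*Protocol*

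**What the plan says.** **Outcome follow-up.** Protocol Section 4.3.1.3 gives the rule: "Women who report being pregnant in the first 3 months of follow-up after the prime vaccination will be followed" to the outcome of the pregnancy. Section 5.4 repeats the trigger ("Women who report being pregnant in the first 3 months of follow-up after the prime vaccination") and puts the outcome on a CRF. The schedule in Appendix A lists "Pregnancy outcome for women who become pregnant in the first three months of follow-up after prime vaccination". The first two count from the date of report and the third from the date of becoming pregnant. All three windows start at the prime.

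**Contraception period.** The synopsis (Procedures) states: "Women of childbearing potential will be told to use adequate birth control measures following randomization and until at least 3 months following the booster vaccination". Section 3 also counts 3 months from the booster. Section 3.2 allows the booster on Day 53 to Day 66.

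**Other capture.** Section 3.3 has staff ask at every follow-up visit about unreported SAEs and, for women, pregnancy. Pregnancy tests are scheduled only at baseline and on Day 56 before the booster. Section 4.1.3 lists as an SAE "Congenital anomaly or birth defects in the offspring of a study participant". Section 4.3.1.3 asks for an SAE form when a pregnancy event or birth outcome qualifies. SAEs are collected to the end of the study (Section 4.3.2) and followed until resolved or stable (Section 4.3.3).

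**SAP.** Section 2.1.5.7 tabulates pregnancies discovered in the 30 days after the prime or booster, with their outcomes. Section 2.1.5.1 defines the primary safety endpoint as SAEs over 12 months.

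**The concern.** The protocol gives a second dose at about Day 56 and asks women to avoid pregnancy for 3 months after it, yet the rule for learning how a pregnancy ended is timed from the first dose. Conceptions after the second dose are the ones most exposed to that cutoff. The two wordings add a practical problem: sites reading different parts of the protocol would follow different women.

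The data are scarce. Section 1.1.3 describes rVSVΔG-ZEBOV-GP as replicating, says its developmental and reproductive toxicology studies were still under way, and notes that pregnant women were excluded from earlier trials. Any statement about losses or anomalies after vaccination needs all outcomes of the exposed pregnancies, the uneventful ones included.

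**Working it through.** This is date arithmetic plus a comparison of the three wordings.

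**Inputs**
- Booster: Day 53 to Day 66, nominal Day 56 (Protocol 3.2).
- Three months: 91 days. This is an assumption, checked at 90 and 92.
- Conception to term: 266 days. This is also an assumption; the documents give no figure.

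**The protocol's own figure.** Month 3 minus the nominal booster day = 91 − 56 = 35 days. This matches the approximately 35 days in Section 3.3. The approximately 28 days in Section 2.6 lies inside the range below.

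**Close of outcome follow-up, in days after the booster**
- 91 − 66 = 25 to 91 − 53 = 38 days.
- With 90-day months: 24-37. With 92-day months: 26-39.

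**Close of the contraception period**
- 53 + 91 = Day 144 to 66 + 91 = Day 157 (Day 147 for a Day 56 booster).

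**Gap**
- 144 − 91 = 53 days to 157 − 91 = 66 days. The gap equals the booster day, so the assumed month length cancels.
- If 3 months means the Month 3 visit (±14 days, Section 3.3, centred on Day 91), the cutoff is Day 77-105. That is 77 − 66 = 11 to 105 − 53 = 52 days after the booster. The gap is then between 144 − 105 = 39 and 157 − 77 = 80 days.

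**Who has required outcome follow-up**

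| Conception | First reported | 4.3.1.3 and 5.4 | Appendix A |
|---|---|---|---|
| Before Day 91 | By Day 91 | Yes | Yes |
| After booster, before Day 91 (e.g. Day 80) | Month 6 | No | Yes |
| Day 91 to Day 144-157 | Any time | No | No |

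The second row is where the passages contradict each other. The third is the gap under either wording.

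**Reach into the 12-month SAE endpoint**
- Latest conception reaching term by Day 365: 365 − 266 = Day 99.
- Conceptions on Day 91 reach term on Day 357. Those on Day 144-157 reach term on Day 410-423.
- So only about the first 8 days of the gap (99 − 91) can yield a term birth inside the endpoint.

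**SAP window.** 53 + 30 = Day 83 to 66 + 30 = Day 96. For boosters after Day 61 it runs past Day 91, by up to 5 days, so it matches neither protocol period.

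**The case against.** The best case for leaving the text alone has four parts.

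1. *The detail sits elsewhere.* Section 4 opens by referring pregnancy and pregnancy-outcome reporting to a manual of operations and calls its own text a summary. Section 4.4 lists pregnancy outcomes for CRF reporting without a time limit. The manual may well say more. But the protocol states an explicit window in three places, and a reference to a manual does not override or reconcile it.

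2. *Serious outcomes are captured anyway.* This stands. A reader might infer that losses and birth defects after the window come to light only if someone volunteers them. The documents do not support that: staff ask about pregnancy and unreported SAEs at each visit, and qualifying outcomes are reportable to the end of the study and then followed. A reader might also infer that the birth-defect part of the primary safety endpoint is seriously incomplete. That fails on timing, since most term births from the gap fall after 12 months. Earlier losses can fall inside 12 months, but those that meet the SAE definition are reportable.

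3. *Appendix A already covers conceptions between the booster and Month 3.* True on its wording, but not on that of Sections 4.3.1.3 and 5.4.

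4. *The windows need not match.* No passage says that outcome follow-up must equal the contraception period. Section 1.1.2 describes MVA-BN as non-replicating and cleared within 48 hours in rabbits, and Section 1.1.3 says rVSV viremia resolves within 2 weeks. A shorter window could therefore be argued, but the protocol does not argue it. The length remains a design choice; the conflict in wording does not.

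It is also tempting to size the problem by the 1,200 of 2,800 participants with an active booster (800 + 400). That count includes men and young children and is not a number of women at risk.

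**Conclusion.** The concern holds in limited form. Sections 4.3.1.3 and 5.4 conflict with Appendix A on which date triggers outcome follow-up, and all three anchor the window to the prime alone. Follow-up therefore closes 25-38 days after the booster (11-52 if the Month 3 visit is meant), while the contraception period runs on for a further 53-66 days (39-80 on the visit reading).

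What is lost is systematic outcome follow-up for those pregnancies: normal births and non-serious outcomes, without which reported losses or anomalies have no denominator. Ascertainment of serious outcomes is not removed, and the effect on the 12-month SAE endpoint is small, given 266 days to term.

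The number of affected women cannot be derived. The documents give neither the number of boosted females of child-bearing potential nor a pregnancy rate. This is worth correcting because it is cheap and the data are scarce; it does not threaten the trial's main conclusions.

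**What to change.** - Reconcile Sections 4.3.1.3, 5.4 and Appendix A on one date basis: estimated conception date, whenever the pregnancy is reported.
- Extend the data-collection window to match the protocol's existing contraception period, that is, conceptions from the prime until 3 months after the last study vaccination. For a woman who received no booster this remains 3 months after the prime.
- Record estimated conception date and days since last dose on the pregnancy CRF.
- State in the SAP how its 30-day tabulation relates to the protocol window.

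The SAP was written after 12-month follow-up was complete, so for women already enrolled the missing outcomes would have to be sought at the later annual visits, which SAP Section 2 says are continuing. Where that is not done, the report should state the window that was applied.

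The cost is protocol and CRF wording plus a modest number of extra outcome forms, some of them completed after Month 12. This concerns data collection only and implies no change to contraception advice or dosing.
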